NACC - National Alzheimer's Center Cohort

naPPA – non-fluent / agrammatic Primary Progressive Aphasia

NWRT – Non-word Repetition Test

svPPA – Semantic variant Primary Progressive Aphasia

tDCS – Transcranial Direct Current Stimulation

WAB: Western Aphasia Battery

WAB-AQ: Western Aphasia Battery – Aphasia Quotient

VAMC: Veteran Affairs Medical Center

Study Summary

Title	Using Transcranial Direct Current Stimulation to Reveal Mechanisms of Language Loss and to Treat Progressive Aphasia Associated with FTD and Related Dementias
Short Title	PPA DOD
IRB Number	843286
Phase	Phase 2
Methodology	Double-blind, sham controlled, crossover design
Study Duration	12 months
Study Center(s)	Single-center
Objectives	
Primary – Characterize tDCS treatment mechanisms by identifying responders to stimulation
 
Secondary – Reveal structural and functional brain connections that predict response to tDCS.

Number of Subjects	62

**Main Inclusion and
Exclusion Criteria**

*Between the ages of 45-80
Diagnosis of PPA
Native English Speaker
No additional neurological disease*

**Investigational
Product (drug,
biologic, device, etc.)**

**For Device include
the planned use** *We will be using a commercially available tDCS device manufactured by
NeuroConn.*

**For Drug, food,
cosmetic, etc.
include the dose,
route of
administration and
dose regimen** *Two 5x5 electrodes at 1.5 mA; anode=F7, cathode = O1.*

**Duration of
administration (if
applicable)** *Stimulation will take place over 2 weeks; 10 sessions for 20 minutes each.*

Reference therapy *Sham tDCS*

**Statistical
Methodology** *Linear Mixed Models will be used to compare the performance of subjects receiving real tDCS to subjects receiving sham tDCS on change in WAB-AQ scores.*

Safety Evaluations *Subject reports of adverse events will serve as the primary measure of safety.*

**Data and Safety
Monitoring Plan** *PI will oversee safety and data monitoring*

CONFIDENTIAL

This material is the property of the University of Pennsylvania.

BACKGROUND AND STUDY RATIONALE

This document is a protocol for a clinical research study. This study will be conducted in full accordance with all applicable University of Pennsylvania Research Policies and Procedures and all applicable Federal and state laws and regulations including US and international standards of Good Clinical Practice.

1. Introduction

Primary Progressive Aphasia (PPA), a condition affecting 20-40% of patients with frontotemporal lobar degeneration (FTLD) disorders and a smaller proportion of patients with Alzheimer's disease (AD), is characterized by progressive deterioration of language function (Mesulam, 2001). There are currently three recognized variants of PPA: non-fluent/agrammatic, logopenic, and semantic. Non-fluent/agrammatic (naPPA) and logopenic (lvPPA) variant are both characterized by difficulties with speech-language production; naPPA typically involves grammatical simplification, effortful speech, and speech apraxia, while lvPPA is associated with phonological errors and poor word retrieval/repetition. Semantic variant PPA (svPPA) involves anomia, reduced expressive vocabulary, and single-word comprehension deficits (Gorno-Tempini et al., 2011). All forms of PPA profoundly impact communication ability and impose a significant burden on patients and their caregivers (Riedijk et al., 2006; Mioshi, et al., 2009; Diehl-Schmid et al., 2013; Mioshi et al., 2013). Speech and language therapies for PPA have shown positive but only modest results (Henry et al., 2008; Croot et al., 2009, 2015; Beeson, 2011; Jokel et al., 2014), and medications used to treat dementias are ineffective. Thus, development of new treatments that can reverse, arrest, or significantly slow language loss in persons with PPA would represent a tremendous step forward for those suffering from this debilitating condition.

1.1 Background and Relevant Research

1.1.1 Neurodegeneration in PPA variants

Specific language deficits that emerge in persons with different PPA variants relate to the regions of the left hemisphere language networks that are selectively affected by neurodegeneration (Grossman, 2010). Atrophy is observed in the left inferior frontal lobe and insula in persons with naPPA. Individuals with lvPPA show atrophy of the left posterior temporal and parietal lobes. Semantic variant PPA (svPPA) involves atrophy of the anterior and ventral temporal lobe (Grossman, 2012; 2018; Agosta et al., 2013; Giannini et al., 2017). Thus, each PPA syndrome affects a portion of the neural network supporting language, while other portions of the language network remain relatively preserved. Unfortunately, while our expanding understanding of the anatomic, neural, and functional properties of language networks has enabled greater insight into the neural changes that underlie PPA symptoms, there are no approved therapies that leverage this knowledge in order to advance targeted treatments for neurodegenerative aphasias.

1.1.2 tDCS to treat PPA

Transcranial direct current stimulation (tDCS), a noninvasive brain stimulation technique, is a promising intervention in aphasia. TDCS delivers low-intensity electrical current to the brain through electrodes placed on the scalp. This low-intensity current can produce small shifts in the resting membrane potential of large numbers of neurons which is believed to alter neuronal firing rates and thus modulates patterns of brain activity (Bindman et al., 1964; Stagg & Nitsche, 2011; Rahman et al., 2013). Evidence indicates that repeated stimulation with tDCS can result in lasting changes in cognitive performance (e.g. Ries et al., 2009; Flöel et al., 2012). A number

CONFIDENTIAL

of studies indicate that tDCS may serve as an effective intervention for aphasia (Reviewed in Norise & Hamilton, 2017). In our own prior work, we found that 10 days of tDCS in subjects with post-stroke aphasia resulted in a ~17% improvement in aphasia severity, compared to sham tDCS. This improvement was measured two months after discontinuation of stimulation (Shah-Basak et al., 2016).

To date, only a handful of studies have investigated the utility of tDCS in persons with PPA. An early case study of one individual with naPPA demonstrated improvements in auditory word-picture identification, picture naming, oral word reading, and word repetition in the absence of speech therapy after five days of tDCS applied over the left posterior region and the left inferior frontal gyrus (LIFG) (Wang et al., 2013). Cotelli and colleagues (2014) found that 10 sessions of tDCS over the left dorsolateral prefrontal cortex combined with individualized speech therapy led to improved picture-naming in a small sample of subjects with naPPA who received tDCS compared to sham stimulation; the benefit lasted up to 12 weeks post-stimulation. More recently, a double-blind, sham-controlled cross-over design study involving 12 subjects with svPPA found that bilateral tDCS to the temporal poles transiently improved semantic accuracy in persons with svPPA (Teichmann et al., 2016).

Our lab conducted a pilot study in a small cohort of subjects with PPA (n=6; 4 lvPPA; 2 naPPA) to determine the feasibility of delivering ten sessions of tDCS to the left hemisphere with follow-up testing immediately after, six weeks, and twelve weeks after stimulation. In order to engage the language network during tDCS, subjects performed an unstructured language task during stimulation in which they verbally narrated wordless children's books. We saw significant improvement in measures of speech production, grammatical comprehension, and semantic processing, which persisted up to twelve weeks post-stimulation (Gervits et al., 2016). We next conducted a randomized, sham-controlled crossover pilot study of the same stimulation approach with follow-up testing two and twelve weeks after stimulation. In a cohort of 7 subjects (1 lvPPA; 6 naPPA), we found beneficial effects of stimulation on global language performance (McConathey et al., 2017). Attrition in these studies was low (~15%).

1.1.3 Combining CILT with tDCS

The idea of pairing speech therapy with tDCS is compelling because tDCS is believed to work by modulating existing neural activation patterns, strengthening or weakening their representations via neuroplasticity (Reato et al., 2013; Jackson et al., 2016). By this account, cognitive activities paired with stimulation determine which patterns of neural activity are reinforced by tDCS, and thus which mental abilities are selectively modulated. Domain-specific training tasks have been paired with tDCS to achieve substantive, long-lasting effects (Reis et al., 2009; Friel et al., 2017; Ruf et al., 2017), and stimulation has been successfully paired with therapies in neurorehabilitation studies (Page et al., 2015; de Aguiar et al., 2015; Mortensen et al., 2016; Viana et al., 2014). We believe that tDCS in persons with PPA will be most effective when paired with a behavioral intervention that engages the language system. We have recently shown that pairing tDCS with a 2-week regimen of a semantic feature training therapy (Boyle, 2004; Hashimoto & Frome, 2011) can improve naming impairments in subjects with severe anomia (svPPA or lvPPA, n = 4; AD, n=1; Hung et al., 2017). Other studies in both post-stroke aphasia and PPA demonstrate that pairing behavioral language intervention with stimulation can result in benefits that generalize beyond trained language items, including improvement in more global measures of aphasia severity (Shah-Basak et al., 2015; Gervits et al., 2016). The current project will employ a modified version of constraint induced language therapy (mCILT), which requires subjects to engage with stimuli verbally with increasing degrees of articulatory complexity (Pulvermüller et al., 2001; Maher et al., 2006). Owing to the task demands of the therapy, mCILT is well-suited to patients with speech production deficits (Pulvermüller et al., 2001; Maher et al., 2006; Breier et. Al., 2009) and has been used successfully in patients with

CONFIDENTIAL

naPPA (Hameister et al., 2017). This study also builds upon our prior success using a similar therapy in persons with nonfluent post-stroke aphasia (Shah-Basak et al., 2015; Norise et al., 2017).

1.1.4 Using brain networks to predict tDCS response

Evidence points toward the importance of brain network hubs—nodes that are connected to many other nodes by edges—in neurodegenerative disorders. Nodes with high hub centrality are critical participants in a wide range of network operations supporting cognitive functions (van den Heuvel & Sporns, 2013) and are disproportionately affected in neurological syndromes (Stam, 2014). The tendency for a node to be a hub can be distinguished from more general measures such as network density, the total number of connections in a network, and can be expressed as a hub score, which quantifies the centrality of a node in information processing in a network (van den Heuvel, 2010). Brain regions with especially high hub scores participate in many processing pathways within the brain. Across the spectrum of neurodegenerative disorders, it is suspected that as nodes in critical brain areas are progressively degraded by disease, this is associated with changes in the recruitment of remaining hub nodes (Stam, 2014). Early in the course of degenerative disease, as specific brain regions are selectively affected, it is believed that there is an *increase* in the connectivity of remaining hubs in those regions that partially compensates for lost nodes and helps to maintain performance (Stam, 2014). However, as worsening disease leads to greater node loss, these compensatory changes cannot keep pace with neurodegenerative deterioration, resulting in decreasing hub scores in affected regions (Buckner et al., 2009; Engels et al., 2015). Eventually, when degenerated regions are severely affected, hub scores decline dramatically as the few remaining nodes do not harbor sufficient connections to contribute to networks. In the case of PPA, residual language abilities would then depend on the activity of relatively spared language regions. In a preliminary analysis of 65 subjects with PPA we found that hub scores are indeed decreased in different language centers in PPA variants. Thus, the hub score could serve as a metric in PPA to describe how affected and spared regions impact network functions at different stages of disease. Brain network hubs could also be positively influenced by interventions that enhance their connectivity. We posit that changes in hub scores could also provide a framework for understanding the impact of tDCS on language networks in persons with PPA.

1.2 Name and Description of the Investigational Product

We will be using a commercially available tDCS devices manufactured by neuroConn, the programmable direct current stimulator. This device is powered by rechargeable batteries and includes a microprocessor controlled unipolar and bipolar constant source for stimulation. This tDCS unit has built-in blinding capabilities, which allows the administrator to enter in a numerical code that corresponds with either sham or real stimulation parameters.

1.3 Dose Rationale (if applicable)

Participants will undergo 10 sessions (Monday-Friday, 2 weeks) of tDCS for 20 minutes using a montage where the anode (1.5 mA) is placed over F7 (left frontotemporal lobe) and the cathode will be place on O1 (left occipital) using the 10-20 EEG mapping system. These stimulation parameters adhere to those used in our prior work (Gervits et al., 2016; Price et al., 2016) and other studies of tDCS in PPA (Norise & Hamilton, 2017).

CONFIDENTIAL

This material is the property of the University of Pennsylvania.

2 Study Objectives

2.1 Primary Objective

- To determine the efficacy of tDCS + mCILT in improving language performance in persons with PPA compared to sham tDCS + mCILT.

2.2 Secondary Objectives

- Utilized network analyses to directly interrogate the roles of structural and function connectively in the language network in PPA.
 - Determine whether baseline hub characteristics of the language systems of persons with naPPA/lvPPA, and svPPA influence aphasia severity.
 - Determine whether tDCS induced behavioral effects induce changes in the language network properties.
 - Determine whether structural and functional connectivity features can predict responsiveness to tDCS.

3 Investigational Plan

3.1 General Design

This is a double-blind, sham-controlled, crossover study. Groups will be counterbalanced according to PPA subtype. All participants will undergo baseline language testing and neuroimaging prior to receiving 10 treatment sessions over 2 weeks (Monday-Friday) of either real or sham tDCS paired with mCILT. Immediate post-treatment, 6 week and 12 week follow-ups will be obtained. Participants will then crossover into the second portion of the study whereby they will receive the opposite treatment protocol (real or sham tDCS + mCILT) and an additional 24 week follow-up. Treatment must take place within 2 days to 4 weeks of baseline testing. The overall timeline for each subject's participation is indicated below in Figure 1.

Figure 1: Timeline for each subject

Enrollment	Baseline MRI	Baseline 1	Baseline 2	Treatment	Follow-up	Follow-up MRI	6 week Follow-up	12 week Follow-up	12 week Follow-up MRI	
SCREENING	VISIT 1**	VISIT 2*	VISIT 3*	Visit 4-13	VISIT 14*	VISIT 15**	VISIT 16*	VISIT 17*	VISIT 18**	
- Informed Consent - Screening Forms - Demographics Form	MRI	-CCRSA -WAB 1 -CILT 1 -NWRT -LTROG Oral -PPT Picture -NACC Word Reading -NACC Sentence Repetition	-WAB 2 -CILT 2 -PRT -DDK -LTROG Written -PPT Words -Story -NACC Sentence Reading	tDCS mCILT OR Sham tDCS mCILT	+	- WAB - CILT - NWRT - PRT - LTROG Oral & Written - PPT Picture & Words - NACC Word reading, Sentence Reading & Repetition - DDK - CCRSA - Story	MRI	- WAB - CILT - NWRT - PRT - LTROG Oral & Written - PPT Picture & Words - NACC Word reading, Sentence Reading & Repetition - DDK - CCRSA - Story	-CCRSA -WAB 1 -CILT 1 -NWRT -LTROG Oral -PPT Picture -NACC Word Reading -NACC Sentence Repetition	MRI
~ 1 hour	~ 1 hour	~ 3 hrs	~ 3 hrs	~ 1.5 hrs	~ 3 hrs	~ 1 hour	~ 3 hrs	~ 3 hrs	~ 1 hour	

CONFIDENTIAL

Crossover Baseline	Crossover Treatment	Crossover Follow-up	Crossover Follow-up MRI	Crossover 6 week Follow-up	Crossover 12 week Follow-up	Crossover 12 week Follow-up MRI	Crossover 24 week Follow-up
VISIT 19*	VISIT 20-29	VISIT 30*	VISIT 31**	VISIT 32*	VISIT 33*	VISIT 34**	Visit 35
-WAB 2 -CILT 2 -PRT -DDK -LTROG Written -PPT Words -Story -NACC Sentence Reading	tDCS + CILT OR Sham tDCS + CILT	- WAB - CILT - NWRT - PRT - LTROG Oral & Written - PPT Picture & Words - NACC Word reading, Sentence Reading & Repetition - DDK - CCRSA - Story	MRI	- WAB - CILT - NWRT - PRT - LTROG Oral & Written - PPT Picture & Words - NACC Word reading, Sentence Reading & Repetition - DDK - CCRSA - Story	- WAB - CILT - NWRT - PRT - LTROG Oral & Written - PPT Picture & Words - NACC Word reading, Sentence Reading & Repetition - DDK - CCRSA - Story	MRI	- WAB - CILT - NWRT - PRT - LTROG Oral & Written - PPT Picture & Words - NACC Word reading, Sentence Reading & Repetition - DDK - CCRSA - Story
~ 3 hours	~ 1.5 hours	~ 3 hours	~ 1 hour	~ 3 hours	~ 3 hours	~ 1 hour	~ 3 hours

* Depending on patient's schedule / fatigue levels, language assessment visits may be accomplished over two to three visits instead of one. To reduce burden of extra visits, language assessments may also be completed at day 1 treatment, prior to the start of the treatment itself.

**Depending on patient's schedule / fatigue levels, MRI visits may be combined with another visit.

3.1.1 Screening Phase

Subjects will be recruited from the large, well-characterized research cohort of the Penn FTD Center. Interested subjects will participate in a brief telephone screening to ensure that they meet basic study criteria including but not limited to age-range, geographic location and native language. Potential subjects eligible based off these criteria will be invited for a formal enrollment appointment where consent will be documented and more in-depth screening will take place. The enrollment appointment will be conducted in-person by the PI or a member of the research staff. Written consent will be obtained before formal screening documents are completed.

A remote screening visit may be conducted via Bluejeans. Before screening interview begins, remote consent will be obtained, with e-signatures collected via RedCAP.

3.1.2 Baseline Phase

The baseline phase will consist of 2-3 sessions, each lasting about 2-3 hours depending on the subject's stamina. The purpose of baseline testing is to characterize the subject's language

CONFIDENTIAL

function. To that end, a number of standard language assessments will be administered. These include the Western Aphasia Battery (WAB), Pyramids and Palm Trees (PPT), Philadelphia Repetition Test (PRT), Non-word Repetition Test (NWRT), CILT stimulus naming, Linguistics Test for Reception Of Grammar (LTROG; written & oral), Diadochokinetic (DDK), Spontaneous story telling (Cinderella Story), National Alzheimer's Center Cohort (NAAC) tests, and Communication Confidence Rating Scale for Aphasia (CCRS). Depending on PPA severity, we may have to split these tests over two-three visits instead of one to accommodate for subject fatigue. Additionally, a baseline MRI scan of the brain will be conducted. No contrast will be used.

Baseline visits might be conducted via tele-assessment, using Bluejeans, or a HIPAA compliant alternative. In such cases, testing materials may be mailed to participants beforehand, and instructions provided during the tele-assessment. Other test materials will be displayed over the video software. Video and audio of the tele-assessment will be recorded.

3.1.3 Study Intervention Phase

In the treatment phase, there will be 10 sessions of tDCS + mCILT over 2 consecutive weeks (Monday-Friday) in which 20 minutes of 1.5mA tDCS will be delivered to the left hemisphere. During each treatment session, a 60-90 minute session of mCILT will be simultaneously performed.

3.1.4 Follow up Phase

There will be an immediate, 6-week and 12-week follow-up following both the initial component. The crossover component will have an additional 24 week follow-up. The full language assessment will be repeated at each follow-up. Subjects will also be asked to complete an MRI scan at the immediate and 12 week follow-ups. Depending on the patients stamina, language assessments may take three visits.

The follow-up visit may be conducted via tele-assessment.

3.1.5 Allocation to Interventional Group

Participants will be semi-randomized using a predetermined list generated by excel. Since this is a crossover study, all participants will eventually receive real stimulation - only the order will differ. Half of our participants will receive real tDCS first, and the other half will receive sham tDCS first. All participants will participate in mCILT.

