5.3 Storage

The tDCS unit will be stored in a locked room in Goddard Labs in which the lab's devices are stored. Only the PI and other members of his research team have keys to this room. When not in use, the unit will be enclosed in a special, dedicated storage container that will be marked

CONFIDENTIAL

with a statement that the enclosed unit is not to be used for clinical purposes. Additionally, the unit itself will be clearly marked with a statement indicating that it is an investigational instrument only.

5.4 *Blinding*

tDCS units have a built in blinding feature via the use of assigned codes which will run specific device parameters.

A master excel file of subjects assignments will be kept by the un-blinded study coordinator. When a subject is randomized, the research team will receive a code to enter into the tDCS unit prior to stimulation. This code will run either a real or sham session. The blinding may be broken in the case of an emergency. To request un-blinding the PI will be informed of the reason for un-blinding and if in agreement will allow the coordinator to tell the researcher what the code means.

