8.5 Subject Population(s) for Analysis

The population that will be subject to analysis will be the full randomized with crossover population. Subjects that are non-compliant with treatment/crossover will be encouraged to continue with follow-up and these measurements will be enter into analysis.

9 Safety and Adverse Events

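### Section 3.1.5 does not state a fully random, concealed sequence, although the analysis treats participants as randomised

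*Combined protocol and SAP*

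**What the plan says.** Section 3.1.5 gives the only account of how treatment order is assigned: "Participants will be semi-randomized using a predetermined list generated by excel". It adds the ratio: "Half of our participants will receive real tDCS first, and the other half will receive sham tDCS first". Section 3.1 supplies the only restriction: "Groups will be counterbalanced according to PPA subtype". The design statement in the same section, "This is a double-blind, sham-controlled, crossover study", does not use the word randomised.

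Section 5.4 covers custody and release. "A master excel file of subjects assignments will be kept by the un-blinded study coordinator". Then: "When a subject is randomized, the research team will receive a code to enter into the tDCS unit prior to stimulation". Section 1.2 says the device "allows the administrator to enter in a numerical code that corresponds with either sham or real stimulation parameters".

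The later sections assume randomisation. Section 8.5 analyses "the full randomized with crossover population", section 5.6 speaks of a randomised intervention, and section 9.7 relies on an intention-to-treat analysis.

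**The concern.** The allocation section stops short of saying that order is random. A semi-random, counterbalanced list could be restricted randomisation loosely described, strict alternation, or a list balanced by hand. The documents give no generation procedure, block size, list author or concealment rule that would tell these apart, so the randomised and intention-to-treat descriptions cannot be verified.

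Custody adds to this. The coordinator who holds the file knows every coming assignment, and no section separates that role from recruitment, screening or scheduling. Section 3.1.1 lets the PI or any member of the research staff conduct enrolment, and section 12.5 lets a designee take consent. There is room for judgement in these steps: eligibility after a past TIA is at the PI's discretion (4.2), and treatment may start from 2 days to 4 weeks after baseline (3.1).

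At stake is the primary real-versus-sham contrast on WAB-AQ. PPA is progressive, so change in the second period need not match change in the first. If the two sequence groups differ in that respect because of how people were placed in them, the difference is read as a treatment effect.

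**Working it through.** The plan states no figure on this point, so there is nothing to reproduce. The numbers below are illustrations on stated assumptions.

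**1. What the treatment estimate is.** For each completer let D = (period-1 change) − (period-2 change), each change taken from that period's own baseline, as section 6.4.6 provides. With treatment effect τ and period difference π:
- real first: mean D = π + τ
- sham first: mean D = π − τ
- estimate = (mean D real-first − mean D sham-first) / 2 = τ

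If mean D also differs between the sequence groups by d for reasons other than tDCS, the estimate becomes τ + d/2. For example, d = 2 points gives a bias of 1 point.

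**2. What cancels.** A participant who loses r points in each period has D = (−r) − (−r) = 0 apart from treatment, whatever r is. Steady decline therefore contributes nothing to d, even if all the fast decliners are in one sequence.

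**3. What does not cancel.** Assume no true effect. Half the participants are slow decliners (−2 points in each period). Half are fast decliners (−4 in period 1, and in period 2 either −4 or, if accelerating, −6). Slow decliners are placed real-first with probability g and fast decliners with probability 1 − g.
- Fast decliners steady: D = 0 for everyone, so the bias is 0.
- Fast decliners accelerating: D = 0 (slow) or 2 (fast). Bias = [2(1 − g) − 2g] / 2 = 1 − 2g.
- First period only: [−2g − 4(1 − g)] − [−2(1 − g) − 4g] = 4g − 2.

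| g | Crossover, steady decline | Crossover, accelerating decline | First period only |
|---|---|---|---|
| 0.5 (no steering) | 0 | 0 | 0 |
| 0.6 | 0 | −0.2 | +0.4 |
| 0.75 | 0 | −0.5 | +1.0 |
| 1.0 | 0 | −1.0 | +2.0 |

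Units are WAB-AQ points. Section 8.4.2 uses 5 points as a clinically meaningful change.

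**4. Dropout.** Section 8.3 anticipates 25% attrition without saying when it falls. Anyone who leaves before period 2 supplies only the first condition, so those data compare different people, as in the last column.

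**5. The model.** Section 8.4.1 fits sequence, period, treatment and treatment × period. A two-sequence, two-period layout has four cell means. With the intercept these terms make five columns of rank 4, so treatment × period cannot be separated from sequence. The sequence term absorbs a constant difference between the groups; it does not remove d.

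**6. How guessable a list could be.** If earlier assignments were known, the average best-guess rate would be 100% for strict alternation, 75% for blocks of 2 (50% on the first member, 100% on the second), 71% for blocks of 4, 68% for blocks of 6, 57% for one balanced list of 62, and 50% for simple randomisation. The documents do not say which applies, and staff blind to earlier assignments could not use these rates.

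**The case against.** A list prepared in advance and kept by one un-blinded person is ordinary practice; the fix below also uses one. The research team receives a masked code only when a participant is randomised, and section 5.4 distinguishes the coordinator from the researcher, who learns what a code means only after the PI agrees to unblind. A half-and-half split counterbalanced by subtype is also what 1:1 randomisation stratified by variant would look like if loosely described. All of this stands.

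It also rules out three stronger inferences a reader might draw:
- **That those who enrol can foresee the order.** Advance knowledge is shown only for the coordinator. For others it would need the coordinator to take part in enrolment, a guessable list, or device codes that are recognisably reused. The documents neither state nor exclude these.
- **That the real–sham contrast has no random basis.** The text leaves randomness unstated; it does not rule it out. The crossover itself also removes stable differences between people.
- **That placing fast decliners in one sequence biases the result in itself.** Step 2 shows that it does not among completers. The change between periods has to differ.

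Nor does one-condition data from early leavers show an allocation fault, since it would arise under perfect randomisation too. Allocation matters there because random order is the main protection for that comparison.

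What the objection leaves unanswered is that no section defines the method, separates the list holder from enrolment, or makes codes specific to a participant.

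**Conclusion.** The point holds as a weakness in the stated allocation method. The sequence is not stated to be fully random, its concealment rests on a separation of roles that is never written down, and the later sections rely on randomisation that 3.1.5 does not establish.

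The exposure is limited to three places: sequence groups that differ in how change varies between periods, dropout before period 2, and any first-period comparison. In the first, the bias is exactly half the difference. The 0.2 to 1.0 points (crossover, accelerating decline) and 0.4 to 2.0 points (first period only) rest on assumed decline rates and assumed steering. The documents do not allow the actual size, or whether any steering would occur, to be determined. The cancellation of steady decline assumes that each period is measured from its own baseline. The change is worth making because it is cheap and cannot be made retrospectively for people already allocated.

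**What to change.** In section 3.1.5, replace *semi-randomized* with a computer-generated random sequence in permuted blocks of undisclosed, varying size, stratified by the two variant groups (naPPA/lvPPA and svPPA). State who generates and holds the list, and that this person has no role in recruitment, eligibility, scheduling or testing. In section 5.4, state that a participant-specific device code is released only after eligibility and baseline testing are complete. Align the wording of 3.1 with this.

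Apply it to participants not yet allocated. Describe those already allocated as allocated under the method used at the time, and record how that list was produced.

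The cost is a one-paragraph amendment and a new list, using existing staff or the REDCap system the study already has. The downside is a small chance imbalance in sequence numbers within a stratum. An exact half split within each variant is unattainable in any case, because 31 is odd (15 and 16 at best).
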